STUDY PROTOCOL
Uterotonic prophylaxis after D&E

PI: [name]
University of California, San Francisco

STUDY PROTOCOL

Study Design

We propose a three-arm randomized, double-blinded, placebo-controlled trial of intramuscular MM versus rectal misoprostol versus placebo after D&E to evaluate the effect of prophylaxis on excessive bleeding. All English- or Spanish- speaking women undergoing D&E at San Francisco General Hospital's Women's Options Center (SFGH WOC) between 20 weeks' 0 days' and 24 weeks' 0 days' gestation will be eligible for recruitment. Women will be excluded if they have a pre-operative diagnosis of hypertension, are using protease inhibitors, have known coagulopathy or history of obstetric hemorrhage requiring blood transfusion, placenta accreta, increta or percreta, and any other contraindication to MM or misoprostol use.

Study Procedures

Recruitment: All eligible women will be identified on the pre-operative day by the research assistant, after clinical staff performs an ultrasound to determine the gestational age. For most women, the pre-operative day is one day prior to the D&E. For a minority of women, it is two days prior to the D&E. After eligibility is confirmed, the research assistant will approach the patient prior to dilator placement to explain the study, and obtain consent.

Randomization: On the day of the D&E, women who consented to participate in the trial will be assigned a study number and random assignment to one of three study arms will be made. We plan to use block randomization for two gestational age ranges (1) 20 weeks 0 days to 22 weeks 0 days; (2) 22 weeks 1 day to 24 weeks 0 days. We plan to use a random number table to assign each study number to one of three arms. By randomizing women just prior to the D&E, we will minimize any negative effect on the randomization scheme if women either fail to return for the procedure or withdraw consent prior to the D&E.

Blinding: MM and saline syringes (placebo) will be prepared by the SFGH Pharmacy. Misoprostol tablets and placebo tablets will be prepared by Abbott Laboratories. The MM and placebo syringes will be identical as will the misoprostol and placebo tablets. No clinical providers or research staff will have access to the randomization scheme. Each subject will receive an intramuscular injection and placement of rectal tablets without knowledge of their contents. To assess the quality of blinding, providers will be asked by the research assistant at the end of the procedure to which group they thought a study patient was assigned.

D&E providers: Ten faculty members at SFGH do D&Es at SFGH WOC. All are routine and experienced providers. D&Es are also done by a rotating third-year resident and a first- or second-year family planning fellow. For the purposes of this trial, only faculty members or the second-year family planning fellow will be performing the D&E.

Reimbursement: Women will be given a \$15 gift card for participating in the trial.

Intervention

Women in this trial will be randomized to one of three arms: (1) MM 0.2 mg intramuscular injection and placebo rectal misoprostol, (2) saline (placebo) intramuscular injection and misoprostol 800 mcg rectal, (3) saline (placebo) intramuscular injection and placebo rectal misoprostol at the completion of the D&E. Completion will be defined as immediately after the last suction. At SFGH WOC, it is standard procedure for providers to perform a final suction at the completion of the procedure. Once the provider states that she/he is finished with the last suction, the nurse will administer the intramuscular injection. The assigned tablets will be given to the provider to place rectally. All study drugs and placebos will be prepared identically and labeled as, "Study drug".

Outcomes

Primary outcome: Our primary outcome of excessive bleeding will be measured with a composite outcome that includes measured post-operative blood loss greater than 125 cc or specific interventions done to manage the excessive bleeding (Table 1). Only one of the listed criteria is needed to qualify as a positive outcome. In addition to our primary, composite outcome, we will also record the number of interventions performed for what the provider deems excessive uterine bleeding. We plan to do sensitivity analyses as follows: (1) a dichotomous outcome of 2 or more interventions used versus less than 2; (2) excluding administration of uterotronics and uterine pressure.

We are not aware of any literature measuring blood loss after D&E at 20 to 24 weeks' gestation. In our clinic, we have observed that approximately 95% of women within this gestational age range have a total post-operative blood loss to be less than 125 cc. We are thus considering greater than 125 cc post-operative blood loss to be indicative of excessive bleeding, and thus have included it as one of the criteria for our composite outcome. For uterotonic medications administered or prescribed, we will record the type (misoprostol, hemabate, MM), dosage, and number of doses.

Many cases of excessive bleeding will fulfill more than one criterion listed in Table 1. For example, most women given a prescription for a uterotonic medication at discharge will likely have received a uterotonic medication. In addition, most women with > 125 cc blood loss post-operatively will likely have received at least one uterotonic medication. In order to increase our sensitivity in detecting excessive bleeding, we have included all possible criteria, and will record the number of interventions someone received. Providers who wish to give a uterotonic medication to treat excessive bleeding will be instructed to wait 5 min after the study drug has been given. They will be able to choose any uterotonic as they normally would.

Table 1. Clinical factors included in composite outcome of excessive bleeding after D&E.

Total blood loss > 125 cc (after D&E)	
Secondary outcome: A secondary outcome will be overall blood loss after the D&E. Blood loss will be measured from the start of the procedure, defined as removal of cervical dilators, to the end of the procedure (after last suction). All bleeding that occurs after last suction will be

Transfusion	
Admission for bleeding	
Re-aspiration for bleeding	
Balloon tamponade	
Uterine artery embolization	
Major surgery for bleeding	
At least 1 uterotonic medication given	
Prescription given for any uterotonic medication at discharge	
Uterine compression (uterine massage or manual pressure for 2 minutes	

considered post-operative bleeding. Blood loss will be measured by collecting the blood in a draped bag underneath the patient and by weighing all gauze used during the procedure. To assess post-procedure blood loss in the recovery room, we will also weigh pads and chux from the time of last suction to discharge, then converting grams into milliliters using the specific gravity of blood which is 1.06 grams per milliliter (Figure 1). We will compare mean total blood loss volume (TBLV) after D&E, a continuous outcome, among the three arms. We have successfully piloted this method of measuring blood loss in our clinic.

Figure 1. Measuring total blood loss after D&E

TPW (grams)	Total pad weight = weight of all pads used
TBLW (grams)	Total blood loss weight = Total pad weight – (Dry pad weight * # of pads)
TBLV (milliliters)	Total blood loss volume = Total blood loss weight / 1.06 g/mL

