Statistical Analysis Plan

Uterotonic prophylaxis after D&E

PI: [name]
University of California, San Francisco

Statistical Analysis Plan

We plan to use t-tests for continuous variables and a chi-square analysis for categorical variables for comparison of study groups at baseline. In the event that the groups are not comparable at baseline, we will do a multivariable analysis adjusting for possible confounders. We will do an intent-to-treat analysis as our primary analysis. If a woman is noted to have elevated blood pressure ($>140/90$) at the completion of the D&E, the study drug will be withheld as this would be a contraindication for MM. These women will still be analyzed in their original randomization group to ensure fidelity to randomization's goal of balancing confounders. In addition to computing the dichotomous outcome of blood loss $> 125\text{cc}$ and/or intervention for bleeding, we will also compare the number of interventions listed in Table 1 for each group. We will also do a sensitivity analysis of the composite outcome in which we exclude the more minor interventions for bleeding, use of uterotonic or manual pressure. For our secondary outcome of mean blood loss difference, we will also conduct a per-protocol analysis, comparing those who received any uterotonic medication (placebo plus additional doses as well as intervention arm plus or minus additional doses) versus those who received no uterotonic.

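### Assignment comes before the blood-pressure check that can withhold study drug, so intent-to-treat contrasts shrink by the share withheld, and no planned analysis recovers the effect on the primary composite

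*Protocol*

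**What the plan says.** Four statements fix the order of events.

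- **Assignment.** Protocol, Study Procedures (Randomization): "By randomizing women just prior to the D&E, we will minimize any negative effect on the randomization scheme". The sentence goes on to name the two events it has in mind: "if women either fail to return for the procedure or withdraw consent prior to the D&E".
- **Dosing.** Protocol, Intervention: "Completion will be defined as immediately after the last suction", and "Once the provider states that she/he is finished with the last suction, the nurse will administer the intramuscular injection". The tablets are placed at the same point.
- **Withholding.** The SAP says that if blood pressure exceeds 140/90 "at the completion of the D&E, the study drug will be withheld as this would be a contraindication for MM". The reason given concerns MM only, but the rule is not limited to an arm.
- **Analysis.** SAP: "We will do an intent-to-treat analysis as our primary analysis". For the withheld women: "These women will still be analyzed in their original randomization group".

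Three other statements bear on the point. Protocol, Study Design excludes women with hypertension diagnosed before the operation. Protocol, Study Procedures (Blinding) keeps the assignment from providers and research staff and says that every subject gets both the injection and the tablets; it mentions no withholding. The SAP's per-protocol analysis applies to mean blood loss and compares women who had any uterotonic, including placebo women given additional doses, with women who had none.

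**The concern.** A woman can be randomised, turn out to have raised pressure at completion, receive nothing, and still count in her arm. Since the arm is unknown to staff, this happens alike under MM, misoprostol and placebo. For misoprostol, part of the intent-to-treat result then reflects drug withheld because of a contraindication to a different arm's drug.

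Undosed women have the same expected outcome whichever arm they were assigned to. They contribute no difference to any of the three pairwise contrasts but still count in the denominators. The stake is attenuation and lost power for the effect of giving the drug. The plan makes no allowance for it, and no other planned analysis of the primary composite compares the assigned arms among dosed women.

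**Working it through.** **Plan's own figure.** There is none to reproduce. The documents give no sample size, power, significance level, target difference, composite event rate or expected share withheld. The only rate is that about 95% of women lose less than 125 cc after the procedure; that concerns one component, not the composite.

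**Shrinkage.** Let w be the share withheld. It has the same expectation in every arm, because the decision is blind and precedes dosing. Let p0 and p1 be the composite rates in dosed placebo and dosed active women, and r the rate in undosed women.

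- Placebo arm as randomised: (1 − w)·p0 + w·r
- Active arm as randomised: (1 − w)·p1 + w·r
- Difference: (1 − w)·(p0 − p1)

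The term in r cancels. The same holds for MM against misoprostol.

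**Sample size, general.** With the variance held fixed, n is proportional to 1/difference², so it inflates by 1/(1 − w)²:

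- w = 2%: 1/0.98² = 1.04
- w = 5%: 1/0.95² = 1.11
- w = 10%: 1/0.90² = 1.23

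**Illustration with assumed rates.** Assumptions: composite 30% on placebo and 15% on active, two-sided 5% test, 80% power, one pairwise comparison, equal arms, and undosed women resembling the rest (r = p0). The usual two-proportion formula is

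n = [1.96·√(2·p̄(1 − p̄)) + 0.842·√(p0(1 − p0) + q(1 − q))]² / (p0 − q)²,

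where q = p0 − (1 − w)(p0 − p1) and p̄ is the mean of p0 and q. With everyone dosed, n = 121 per arm. The last column omits withheld women, leaving 121·(1 − w) per arm at the full 15-point difference.

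| w | Active rate as randomised | Power at 121 per arm | n per arm for 80% | Power, withheld women omitted |
|---|---|---|---|---|
| 1% | 15.15% | 79.3% | 124 | 79.8% |
| 2% | 15.30% | 78.3% | 127 | 79.4% |
| 5% | 15.75% | 75.5% | 136 | 78.1% |
| 10% | 16.50% | 70.3% | 153 | 75.9% |

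For a binary outcome the inflation is slightly above the general factor (153/121 = 1.26 against 1.23 at w = 10%), because the active rate moves toward 50% and its variance grows. Assuming 50% against 30% instead (93 per arm) gives nearly the same power: 78.3%, 75.6% and 70.7% at w = 2%, 5% and 10%.

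**Does another planned analysis cover it?** The per-protocol analysis differs in two ways from what is needed. Its outcome is mean blood loss, not the composite. Its groups are any uterotonic against none, so placebo women who received additional doses join the active-arm women. It is not a comparison of assigned arms among dosed women.

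**The case against.** The strongest reply is that the SAP foresaw these women, keeps them in their groups and gives a reason, which is preserving the balance from randomisation. That is sound intent-to-treat practice. It does not bias the estimated effect of assignment or raise the false-positive rate. This stands; the point concerns efficiency and what the plan leaves unestimated.

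The size is also unanchored. Excluding pre-operative hypertension should lower w, and at 1–2% the illustration loses only about 1 to 2 power points. Nothing in the documents supports the 10% row over the 1% row. This stands too.

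A reader might infer that the timing defeats the Protocol's own rationale. It does not: the stated reason covers only failure to return and withdrawal of consent, and assignment just before the D&E serves it. Nor should these women be called screen failures. Eligibility is confirmed on the pre-operative day, and the disqualifying reading exists only at completion.

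A reader might also infer that assigning later is free. The documents describe identically prepared and labelled drugs, with syringes from the hospital pharmacy and tablets from a manufacturer. They do not describe numbered packs held by gestational-age stratum, or say whether syringes are made per patient. Feasibility is therefore open.

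Finally, if the Protocol's statement that every subject is dosed governs, w is zero and the point falls away. What survives is that the SAP as written creates an undosed group and leaves the composite without an analysis that sets it aside.

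**Conclusion.** The point holds as one of attenuation and a missing supporting analysis. As the SAP stands, every between-arm contrast on the composite shrinks by 1 − w, with the required sample size rising by roughly 4%, 11% and 23% at w = 2%, 5% and 10%.

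This rests on three assumptions. The SAP rule must be in force. Withholding must cover both injection and tablets in every arm; the SAP does not spell this out, but the Protocol labels both as study drug. If only the injection were withheld, misoprostol against placebo would not be diluted. For the sample-size figures, undosed women must resemble the rest.

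A reader might go further and conclude that the primary analysis is invalid or the trial seriously underpowered. The documents support neither: intent-to-treat answers the question about assignment correctly, and with no w and no sample size stated, the loss could be negligible. A low-cost addition is still justified.

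**What to change.** 1. **Reconcile first.** Bring the Protocol's Blinding text, under which every subject is dosed, into line with the SAP's withholding rule, and say whether the rule covers both injection and tablets. No view is taken here on the clinical rule.
2. **Add to the SAP.** Keep intent-to-treat as primary. Prespecify a supporting analysis of the primary composite by assigned arm that omits women whose study drug was withheld under this rule, and report the numbers withheld by arm. Because the decision is made blind and before dosing, the omission cannot depend on the arm, so the comparison is unbiased for women not withheld. Record the reading and the decision before study drug is given, so that this can be shown. The cost is a few lines of text and one extra data item.
3. **Where pharmacy supply allows, amend the Protocol's Randomization text.** Note the gestational-age stratum beforehand, but assign the study number and study drug after the last suction and the pressure check. Every randomised woman then stays in the intent-to-treat analysis without this dilution. The cost is that study drug for the stratum must be at hand at completion and may occasionally go unused.

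### Must the plan spell out whether a discharge uterotonic prescription is dropped from the reduced-composite sensitivity analysis?

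*Protocol*

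**What the plan says.** The protocol's primary outcome is a composite of ten criteria in Table 1, and "Only one of the listed criteria is needed to qualify as a positive outcome". Three of the ten matter here:

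- "At least 1 uterotonic medication given"
- "Prescription given for any uterotonic medication at discharge"
- "Uterine compression (uterine massage or manual pressure for 2 minutes"

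Under Outcomes, the protocol's second sensitivity analysis is defined only as "2) excluding administration of uterotronics and uterine pressure". The SAP describes the same analysis as one in which "we exclude the more minor interventions for bleeding, use of uterotonic or manual pressure". Neither text mentions the prescription row.

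On data capture, the protocol states "For uterotonic medications administered or prescribed, we will record the type", along with the dosage and the number of doses. It also expects most women who leave with a prescription to have been given a uterotonic already.

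**The concern.** The protocol speaks of administration, and elsewhere under the same outcome it names administering and prescribing as two different acts. Taken strictly, the exclusion reaches only the row for a uterotonic given. The prescription row stays in and, because one criterion is enough, it brings back some of the women whom the exclusion was meant to remove. The SAP's reference to use of a uterotonic could be read either way.

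There is a similar looseness about compression. Table 1 covers massage and manual pressure in one row, while the two exclusions mention only pressure.

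The analysis exists to show whether a treatment effect depends on discretionary, milder responses to bleeding. If two analysts could classify the same women differently, the answer might depend on who ran it. A choice made after the allocation was known could also be questioned.

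**Working it through.** The plan gives no event rate, sample size or power figure for this analysis, so there is no stated figure to reproduce. The check compares the texts, counts rows and adds a rough scale.

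**Rows kept under each reading** (inputs: Table 1 and the two exclusion phrases)

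| Reading | Rows dropped | Rows kept |
|---|---|---|
| Literal protocol | given, compression | 10 − 2 = 8, including prescription |
| Following the SAP's aim | given, prescription, compression | 10 − 3 = 7 |

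The seven rows common to both are blood loss above 125 cc, transfusion, admission, re-aspiration, balloon tamponade, embolization and major surgery.

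**Where the readings differ.** A woman positive on any of the seven is positive under both. If all seven are negative, the other three rows form 2³ = 8 combinations. The literal reading scores the 2² = 4 combinations that include a prescription as positive; the SAP-based reading scores none. These are patterns, not patients, and say nothing about frequency.

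**Which reading fits the text.** Consider what each reduced composite would contain. The seven-row version consists of measured blood loss and serious interventions. The eight-row version adds one item, a take-home prescription, after removing a dose given in the clinic. That would be an odd way to set aside the more minor interventions, which is the purpose the SAP states. A prescription also falls easily within use of a uterotonic. The protocol sentence that names both administering and prescribing is a data-recording statement; it does not make administration a defined term in the sensitivity analysis.

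**Compression.** Only one Table 1 row involves pressure on the uterus, and massage belongs to that same row. Both short phrases can refer only to it, and nothing suggests splitting it.

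**Scale.** The only frequency available is the protocol's clinic observation that "approximately 95% of women within this gestational age range have a total post-operative blood loss to be less than 125 cc". This puts the blood-loss criterion at about 100% − 95% = 5%. Assume that this holds in the trial and ignore the other six rows. Let *x* be the share of all women who have a prescription and none of the seven rows; the documents give no value for *x*.

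- Rate under the SAP-based reading: about 5%.
- Rate under the literal reading: 5% + *x*, which is 6%, 10% or 15% for assumed *x* of 1%, 5% or 10%.
- Relative increase per point: 1/5 = 20% on a base of 5%. On a base of 4%, which is possible because two of the three arms receive prophylaxis, it is 1/4 = 25%. The 20% is therefore not an upper limit.

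**Precision.** Dropping a row gives fewer events, but that does not always widen the interval. For a risk difference the standard error scales with √(p(1 − p)): √(0.05 × 0.95) = 0.218 and √(0.06 × 0.94) = 0.237, so the lower rate gives the narrower interval. For ratio measures it goes the other way. The documents name no effect measure, so precision does not favour either reading.

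**The case for a change.** The best case for a change is that the ambiguity is real and cheap to remove. The two documents describe one analysis in different words, and neither refers to Table 1 by row. The literal reading is a fair reading of the protocol sentence. The protocol's own expectation that prescriptions mostly follow a dose means that the retained row would bring back exactly the women in question. One sentence in each document would settle it and would remove any suspicion of a choice made after unblinding.

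The textual part of this stands: neither document names the prescription row, and the authors' intention is inferred, not stated. The consequence does not follow. The SAP's purpose gives an analyst enough to choose, and the choice can be reported by listing the rows used. Doses and prescriptions are both recorded, so anyone who prefers the other reading can be shown that result too. Providers treat and prescribe under double blinding, so either rule is applied identically across arms. The risk of a selective choice is confined to one supportive analysis and cannot reach the primary result.

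**Conclusion.** This is imprecise shorthand in one sensitivity analysis, a gap that a sensible analyst fills from the SAP's stated aim: drop both uterotonic rows and the compression row, and keep the other seven. The literal reading is possible but is the weaker one once the two documents are read together, and the supposed gap about massage is not a real one.

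The effect on this analysis cannot be quantified, because no prescription rate is given. The step from 5% to 6% per percentage point rests on the approximate clinic figure carrying over to the trial and on the other six criteria being rare. The primary composite and the trial's main conclusion do not depend on the point under either reading. Naming the rows when the result is reported is ordinary good practice and does not require an amendment.
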